Aim 2: Determine efficacy of initiating the exercise intervention 6 wks post-discharge and compare results with the immediate intervention group by age. Hypothesis 2: The immediate exercise intervention group will improve for all ages at a greater rate and magnitude than the wait-list group for all outcomes.

Aim 3: Determine the immediate exercise intervention's sustainability by analyzing a) rates of extension, adherence, and retention; b) acceptability; and c) efficacy of primary and secondary outcomes. Hypothesis 3: The exercise intervention will be acceptable with >50% extending at wk 6 and >70% adherence and retention at wk 12, with improved primary and secondary outcomes at wk 12.

IMPACT: Our results will provide a novel, practical, portable, low-cost, and enjoyable exercise intervention with important information on its optimal timing and sustainability to fill the gap regarding approaches that are applicable to nearly all post-thoracotomy lung cancer patients for reducing CRF severity and fatigability.^{20,22,27-32}

Section 2.0 Introduction

Significance

2A) OVERALL SCIENTIFIC PREMISE

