Lung cancer is the most common cancer worldwide (1.8 million cases/year, NSCLC accounting for ~85% of cases).⁷⁰ The 5-year survival rate for lung cancer is 55% for cases detected early⁷⁰ with surgery being the best curative treatment; CRF is reported as the most prevalent and distressing symptom in this population.^{35,52,71} This research addresses a glaring knowledge gap in how to rehabilitate and treat CRF in this sizeable, high acuity cancer population.^{8,35} Based on existing evidence,⁷²⁻⁷⁵ results of our single-arm pilot (no control group)^{76,77} and two-arm R21 RCT,²³ we expect the benefits of this study to confirm that post-surgical NSCLC patients will find the exercise intervention effective in reducing CRF severity and fatigability (functional capacity). Further, we expect the exercise intervention group will outperform the attention control and wait-list control groups by age for other symptoms' severity; PSE for CRF self-management; PSE for walking; PSE for balance; functional performance; and QOL. We expect the wait-list exercise intervention group's CRF severity and fatigability to improve, but not as significantly as the immediate exercise intervention group. We also expect >50% of the immediate exercise intervention group to extend 6 more wks, with adherence and retention rates of >70% at wk 12, with improved primary and secondary outcomes at wk 12. Once this exercise intervention's effectiveness is further demonstrated, the intervention will provide a practical and portable means to treat CRF severity and fatigability for NSCLC and other vulnerable populations transitioning from hospital to home.

Innovation

2E) TRANSFORMING THE STATUS QUO

This study is the first extensive study to target and analyze by age a priority symptom, fatigue and its associated fatigability, in a vulnerable, underserved post-thoracotomy NSCLC population during their transition from hospital to home. Our proposed research builds on the results of our single-arm pilot and

two-arm RCT. The approach executes transitional care principles to address a high-risk, high-cost, high-volume patient population and their most critical reported unmet needs. We will assess the timing and the corresponding sustaining effects of the exercise intervention in order to help define its optimal delivery.

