use/effectiveness throughout the post-thoracotomy NSCLC population's survivorship trajectory.¹⁰⁴ Sustainability is defined as the continued use beyond the initial implementation of the intervention for the continued achievement of desirable outcomes for the intended population.¹⁰⁴⁻¹⁰⁶ Little research has been conducted with the post-thoracotomy lung cancer population on how to *sustain* changes in exercise behaviors and their associated effects over time for CRF, functional status, and QOL.^{27-29,69} Cochrane reviews²⁷⁻²⁹ state that research is required to investigate how to sustain these positive effects and determine the attributes that lead to success—a key goal of intervention science—to understand if investments are leading to longer-term beneficial outcomes.¹⁰⁴ The design of the proposed exercise intervention combines recommended attributes identified as potential motivators to promote a sustained exercise intervention in the cancer population. These exercise motivators include but are not limited to: use of self-efficacy theory to create intrinsic demand for the intervention;^{29,89} use of a home-based approach³⁰ with service delivery, including face-to-face contact followed up with phone contact;¹⁰⁷ use of informational motivators such as activity logs; portable heart rate monitors and pedometers; and expert consultation provided by qualified health care providers.⁸²

Fig 2: RCT Participant Demographics

Mean age = 67 yrs (range 32-89 yrs)
56% female
74% married
56% retired
29% employed outside home
89% White
7% Black (n = 5)
4% American Indian (n=3)
19% did not complete HS
43% completed HS only
28% some college or post-HS training
10% college and/or post-grad

PRELIMINARY WORK

2N) Two-Arm R21 RCT Pilot Published 2017^{23,24}

Purpose. Examine feasibility, acceptability, and preliminary efficacy of a rehabilitative intervention for CRF severity, fatigability, PSE for fatigue self-management, other symptoms' severity, PSE for walking & balance, and functional performance for post-surgical NSCLC patients.

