Methods. Participants (Figs 2, 3) were randomly assigned prior to surgery to intervention group (IG) (n = 37) or usual care group (UCG) (n = 35). The IG performed prescription-based virtual reality walking and balance exercise using the Nintendo Wii in their home. The 6-wk light-intensity exercise intervention was self-paced, gradually building in duration upon hospital discharge after NSCLC surgery. A nurse called the participant within 24 hrs post-surgical hospital discharge to screen for readiness to start the intervention. A home visit to start exercise was scheduled within 4 days of discharge. The nurse made a second home visit at the start of wk 2 and phone visits at the start of wks 3-6, with additional visits on participant request. Both home and phone visits supported participants by providing PSE-enhancing CRF self-management interventions to support exercise and adjust the exercise prescription

Aim 1 Results (feasibility, acceptability, safety) Recruitment.

We recruited 67% of eligible participants, exceeding our goal of 50%. Also, recruiting goals of N=64 were exceeded: 72 participants completed the study, recruited from one hospital site in west Michigan and two hospitals in mid-Michigan.

Retention, adherence, acceptability, & adverse events:

Retention was assessed by measuring percentage completing the program from first phone visit after surgery to final data collection at wk 6. Even though this vulnerable population had a mean of 8 comorbid conditions, the goal of 70% retention was exceeded: 97% of participants completed the intervention.

Adherence was measured by computing percentage participating in the intervention that adhered to the recommended intervention. The goal of 70% adherence was exceeded, as 37 participants adhered to their prescribed exercise at a rate of 93%. Acceptability was assessed via a 15-item questionnaire providing feedback in multiple areas. The 37 participants gave a mean rank of 5.6 (scale 0-6, 6 = highest acceptability) exceeding our goal of a mean positive acceptability score of 4. Participants stated that the intervention was enjoyable and effective in helping control their fatigue. A proposed improvement was after 10 mins of walking with the Wii, participants wanted the option to walk outside or in another venue; this is now incorporated in our proposed intervention. No adverse events were reported.

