
Section 5.0 Research Design

5A) Introduction to the Research Design of Proposed Project

We propose a three-arm, repeated measures RCT for persons undergoing NSCLC surgery as shown in **Fig 8**. The design provides for **efficacy** comparisons of outcome measures among the immediate (exercise) intervention group (IIG), the wait-list control group (WCG) usual care, and the attention control group (ACG) by age after 6 wks (**Aim 1**) through the measurement of primary and secondary outcomes. The design also provides for evaluation of the timing of the intervention (**Aim 2**) by comparing study outcomes of the IIG's wks 1-6 with those of the WCG's wks 7-12 by age to account for time since surgery. Note that the timing of the data collection occurs near the time of the assessment during the week when the assessment is conducted. For example, if a participant has an unexpected visitor at their home and would like to have the data collector call the next day, then the data collector may call the next day. Unlike mice or non-human studies, we need to balance absolute timing against the needs of our human participants so we incorporate some flexibility required of our human participants when collecting data. Determining optimal timing to initiate an exercise program for post-surgical NSCLC patients is needed. We chose to start the WCG intervention at 6-wks post-hospital discharge based on Leach et al.'s¹¹³ findings that 43% of the 66 postsurgical NSCLC patients in their study preferred to start an exercise program during adjuvant treatment. Also, adjuvant treatment (radiation and/or chemotherapy) commonly begins 4-10 wks after surgery, with nearly 30% of patients undergoing adjuvant treatment¹¹⁴ Sustainability of the intervention (**Aim 3**) can be determined by offering the IIG the option to extend their exercise to 12 wks and calculating the percent that elect to extend, assessing acceptability, adherence, and retention while measuring primary and secondary outcomes for efficacy. Adverse events will be monitored to provide for safety (R21 RCT reported no adverse events).

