5C2) Study Procedures. IIG participants will have baseline data collected by the nurse recruiter. Following principles of transitional care,¹²⁴ the exercise nurse intervener will engage the participant using protocol in Appendix A4 in the hospital post-surgery to review the exercise intervention and teach PSE-enhancing CRF self-management education (Appendix A5) that uses National Comprehensive Cancer Network Guidelines.¹²⁵ To ensure continuity, a primary nurse will be assigned to each participant. Data collectors will contact IIG by phone within approximately 24 hrs of discharge to collect data (if too ill, re-scheduled within approximately 3 days of discharge) and at approximately the end of each week for 6 wks. The nurse will make a phone visit within approximately 24 hrs of post-surgical discharge to screen participant’s readiness to start exercise. Participants will be deemed ready to start if usual level of severity for key symptoms of pain, nausea, and dyspnea are rated ≤ 4 on an 11-point scale (0-10, 10 = most severe). If participant is ready to exercise, a home visit will be scheduled to start exercise within approximately 4 days of discharge. When severity of a key symptom is rated > 4 , nurse will intervene and contact participant’s surgeon’s office for recommendations. The nurse will repeat this step each day until participant is ready to start exercising. Once participant is ready, nurse will arrange home visit within approximately 3 days. The initial home visit will include connecting Wii to participant’s TV, setting up Wii FitPlus log on password, teaching exercise intervention, and reinforcing CRF self-management education and exercise safety precautions. The nurse will follow-up with phone visit within approximately 24 hrs to answer questions and concerns, make a follow-up home visit at approximately the start of wk 2 of exercise, phone visits at approximately the start of wks 3-6, and additional visits per participant request. During visits, nurse will review IIG participant’s Daily Diary (Appendix A2) with participant and provide PSE-enhancing CRF self-management interventions (Appendix A6). These PSE-enhancing interventions include providing mastery and/or vicarious experiences; social encouragement; and reinterpretation of physical and psychological symptoms to support exercise program to adjust exercise prescription per guidelines. Participant uses Daily Diary to record weekly exercise activity and exercise-related symptoms or issues. IIG participants will be given the option to extend exercise for another 6 wks to study wk 12. Data collection will continue on a weekly basis, culminating with a 6MWT at end of approximately wk 12. Nurse calls will continue weekly to prescribe balance exercises and advance walking prescription 5 mins each week, with goal of achieving minimum 30 min/day. Participants may extend beyond 30 min/day with rate of increase no more than 5 min/day each wk, with participants’ PSE for attaining that duration $\geq 70\%$ on a 0-100% scale (100%=high PSE) (Appendix A1).

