Perceived Self-Efficacy	Pain Self-Management	The Perceived Self-Efficacy for Pain Self-Management Inventory (6 Items)	Pre & Post-Surgery Weeks 3, 6, 9, 12	Degree of pain self-management. (0.90)

Aim 2 – Measures – WCG Delayed Intervention. At the start of wk 7, WCG will begin the intervention, concluding at wk 12. Aim 1 study variables and measures (Table 3) will be analyzed for Aim 2 for wks 7-12 to compare with the IIG wks 1-6 outcomes.

Aim 3 – Measures – IIG Intervention Sustainability. At the start of wk 7, IIG participants will be given the option to extend the intervention an additional 6 wks. We will measure the extension rate as % participants who elect to extend. Adherence to the intervention will be measured as % participating in the intervention who adhered to prescribed intervention. Weekly adherence will be calculated by taking number of times prescribed intervention was completed divided by total number of interventions prescribed for week. These data are recorded in the Daily Diary and will be confirmed by research staff reviewing recorded data in Wii Fit-Plus. Retention, measured as part of sustainment, will be calculated as % who elected to extend 6 wks who completed final data collection at wk 12. Based on our conceptual definition of sustainability, we will measure the extent to which components of the intervention were rated acceptable for continued use by participant. Acceptability will be measured at end of wk 6 and 12 using a 15-item Acceptability Questionnaire (Appendix B1) using a numeric scale (1 to 6: 6 = agrees strongly) with higher scores indicating greater acceptability of the exercise program. The Questionnaire has a Flesch-Kinkaid 6th grade reading level and was successfully used in our R21 RCT and allows participants to rate how well barriers and facilitators to exercise are addressed. Open-ended questions provide further input.^{23,24} Efficacy will be measured using the same study variables and measures analyzed in Aim 1 (Table 3) for wks 7-12.

Section 8.0 Drug Formulation and Procurement

Not applicable. This study is not a pharmaceutical trial.

Section 9.0 Toxicity and Adverse Event Reporting Guidelines

Study Monitoring

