AEs will be collected from the time the subject signs the consent form until 30 days after the final protocol specified intervention. All AEs will be followed until resolution or a cause is identified. AEs judged by the investigator as not related or probably not related to the treatment will NOT be followed beyond the end of the study.

Section 10.0 Statistical Considerations

Statistical Analysis. All tests of hypotheses will be two-tailed at $\alpha=0.05$. We compare groups at baseline using parametric and non-parametric tests to assess equivalence of confounding physiological and contextual patient characteristics, and pre-surgical outcome variables. If substantive differences exist, they will be controlled for in subsequent analyses by regression techniques, guided by the degree of dissimilarity rather than strict statistical significance.¹⁴⁴

Primary analysis (Aim 1) is the comparison among study groups of the primary outcome CRF severity and fatigability assessed at approximately 6 wks post-surgery. Analysis is based on a regression model for both CRF scores with the following variables in the regression equation: baseline CRF, study group, age, and (if appropriate) plausible interaction between these variables. We test association of study group with outcomes.

In Aim 2 our hypothesis comparing outcomes in IIG and WCG by age group will be addressed in the context of a longitudinal analysis. There are 6 time-ordered differences between IIG and WCG. We use generalized linear (mixed) models to allow flexible correlation structures in the repeated measures.^{145,146} Our regression equation has in addition to the aforementioned variables: time (week) of assessment, and critically, study group with time interactions. The model allows us to test if group effects are changing over time – referred to as a “parallel” profile analysis.¹⁴⁷ If the hypothesis is supported, we test whether that average profiles (over time) in

the two groups are the same. Aim 3 concerns three binary responses in the IIG group at 6 wks: extension, retention, and adherence. Logistic regression models will be used to assess the influence of explanatory variables on the likelihood of outcome.¹⁴⁷⁻¹⁴⁹

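### Section 10 analyses Aim 3 retention and adherence at 6 weeks, although Hypothesis 3 sets both at week 12 and retention as defined in Section 7 cannot be observed at week 6

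*Combined protocol and SAP*

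**What the plan says.** Section 10.0 (Statistical Considerations) introduces the sustainability analysis with "Aim 3 concerns three binary responses in the IIG group at 6 wks: extension, retention, and adherence". The method it names is logistic regression on explanatory variables.

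Elsewhere the timing differs:

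- Section 1.0, Hypothesis 3: "with >50% extending at wk 6 and >70% adherence and retention at wk 12".
- Section 2D (Expected Benefits) and Section 6.0 (Measurement of Effect): "with adherence and retention rates of >70% at wk 12".
- Section 7.0, Aim 3 measures: retention "will be calculated as % who elected to extend 6 wks who completed final data collection at wk 12". Adherence is calculated weekly from the Daily Diary. The option to extend is offered at the start of week 7.
- Section 5A: sustainability is to be determined by, among other things, "calculating the percent that elect to extend, assessing acceptability, adherence, and retention".

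Under Secondary Outcomes, Section 10.0 says openly that the 12-week models are conditional on choosing to extend. It then commits to both intention-to-treat and per-protocol analyses.

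**The concern.** The analysis section is what a statistician will program from. Read literally, it takes all three responses at week 6. Extension is correctly placed there. Retention and adherence are not, and for retention the definition makes week 6 impossible, because the numerator is completion of data collection six weeks later.

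The likely harm is a quiet substitution of week-6 completion and week-6 adherence, which are different quantities. That is easy to imagine, because the pilot in Section 2N did measure retention over six weeks and reported it against a similar goal: "the goal of 70% retention was exceeded: 97% of participants completed the intervention". A week-6 rate would describe the initial programme. Aim 3 asks whether participants keep going after it.

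A second, smaller matter is the denominator. Retention is counted among extenders only, and Section 7.0 does not say whether extension is counted over everyone randomised to the arm or over those still present when the option is offered. Section 2M describes sustainability as continued use in order to secure "the continued achievement of desirable outcomes for the intended population". A reader will want to know what share of the randomised arm the rates represent.

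**Working it through.** **Time points side by side**

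| Response | Hypothesis 3 (1.0; also 2D and 6.0) | Section 7.0 definition | Section 10.0 |
|---|---|---|---|
| Extension | over 50%, week 6 | choice offered at start of week 7 | 6 weeks |
| Adherence | over 70%, week 12 | calculated weekly | 6 weeks |
| Retention | over 70%, week 12 | extenders completing week 12 | 6 weeks |

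Extension agrees throughout. Adherence in Section 10.0 conflicts with Hypothesis 3 and its two restatements. Retention conflicts with these and with its own definition.

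**Size of the denominator effect**

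The documents give no sample size or precision figure for Aim 3, so there is none to reproduce. The counts below are illustrations and not forecasts.

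Inputs: thresholds of 50% and 70% (Hypothesis 3); recruitment target 279 and attrition 20% (Section 5B); 60 per arm in the power calculation (Section 5B). The plan's inflation gives 180/0.8 = 225 and 225/(0.9 × 0.9) = 277.8. This rounds up to 278, or 279 as a multiple of three. With equal allocation (assumed), 279/3 = 93 per arm.

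If extension is counted over all randomised:

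share of arm extending and completing = (extended/randomised) × (completed week 12/extended)

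At exactly the thresholds this is 0.50 × 0.70 = 0.35. Intervals for x out of n are Clopper-Pearson. The lower limit is the 2.5% quantile of Beta(x, n − x + 1) and the upper limit is the 97.5% quantile of Beta(x + 1, n − x).

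| Case | Extension | Retention among extenders | Share of randomised arm |
|---|---|---|---|
| Bare success, 93 per arm | 47/93 = 50.5% (40-61%) | 33/47 = 70.2% (55-83%) | 33/93 = 35% (26-46%) |
| More favourable, 93 per arm | 65/93 = 70% (60-79%) | 52/65 = 80% (68-89%) | 52/93 = 56% (45-66%) |
| Bare success, 60 per arm | 31/60 = 52% (38-65%) | 22/31 = 71% (52-86%) | 22/60 = 37% (25-50%) |

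Here 47 is the smallest count above 50% of 93, and 33 the smallest above 70% of 47.

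If extension is instead counted over those still present at week 6, a third factor enters:

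share of arm = (present/randomised) × (extended/present) × (completed/extended)

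Assume the full 20% attrition has occurred by week 6, so 0.8 × 93 ≈ 74 are present. Then 38/74 (51%) and 27/38 (71%) both pass, and the share is (74/93) × (38/74) × (27/38) = 27/93 = 29%. The share therefore depends on a denominator that Section 7.0 leaves open.

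**The case against.** The strongest reply is that the phrase in Section 10.0 is loose wording. Three statements of the target and the operational definition all point to week 12, and an analyst could not compute the defined retention rate at week 6 without noticing. Adherence is recorded weekly, so the week-12 data will exist. Aim 3 concerns one arm and does not touch the Aim 1 comparison or its power. All of this stands, and it limits the practical harm. The analysis section still says the wrong thing for two of three responses.

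A reader might infer more than the documents support:

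- *That the plan never sets the rates against the thresholds.* Sections 5A and 7.0 provide for measuring the rates, and a percentage beside a target is a usable benchmark. The pilot judged its goals in that way.
- *That the thresholds must be formally tested because they appear in a hypothesis.* The two-tailed rule in Section 10.0 governs tests that are carried out; it does not oblige the investigators to test every expectation. Whether the thresholds are tests or benchmarks is a missing detail.
- *That adherence cannot be made binary.* The per-person rule may sit in appendices that were not supplied.
- *That the 12-week models breach intention-to-treat.* The conditioning is disclosed as a caveat, and outcomes among continuing users are a legitimate sustainability target. What is needed is a label.
- *That an all-randomised week-12 outcome estimate is required, or that non-extenders are not followed.* The first is a choice of estimand. On the second, Section 5C2 says, after describing the option to extend, "Data collection will continue on a weekly basis, culminating with a 6MWT at end of approximately wk 12", without saying for whom. Section 7.0 has every measure given to all participants on the Table 3 schedule, and Figure 8 shows week 7-12 data collection for the arm without splitting it by extension. Neither settles the matter, because the attention control arm stops at week 6 and Figure 8 shows the whole immediate arm exercising throughout.

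**Conclusion.** The timing conflict is real and rests on the current text alone. Section 10.0 places retention and adherence at 6 weeks; Hypothesis 3 and its restatements place them at week 12, and the retention definition makes any other time point impossible. It should be corrected before analysis, but it does not affect the primary analysis.

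The denominator matter is one of clear reporting. Counted over all randomised, bare success on both thresholds means about 35% of the arm extended and completed (33/93, CI 26-46%). With extension counted over those still present and 20% lost, the example gives 29%. These figures assume 279/3 = 93 per arm with equal allocation and, for the 29%, that all the attrition falls before week 6. They show what the two rates can jointly mean and predict nothing about the trial.

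**What to change.** Needed, in Section 10.0: state that extension is analysed at week 6, and adherence and retention at week 12.

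Cheap additions:

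1. Count extension over all randomised immediate intervention participants, and say so.
2. Report each rate with an exact 95% CI beside its threshold, as a descriptive benchmark.
3. Keep the Section 7.0 extender denominator for retention, and give next to it the share of all randomised participants in the arm who extended and completed week 12.
4. Label the 12-week outcome models as describing extenders and not as intention-to-treat results.

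The cost is a few sentences and one extra line per results table; no data collection is added. The downside is a less favourable figure beside the extender rate (35% against 70%, or 56% against 80%, in the 93-per-arm illustrations), with wide intervals.

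A week-12 outcome estimate for everyone randomised to the arm is a suggestion only. It would need a stated estimand: outcomes whether or not people extended, or outcomes had all extended. First, Figure 8, Section 5C2 and Section 7.0 (including Table 3) should be reconciled on whether non-extenders are assessed after week 6. If they are not, the estimate would rest on missing-data assumptions and should be reported with that limitation.
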